5.5.12.1.3. Vital Signs and Weight

Vital signs collected during the study include systolic and diastolic blood pressure, pulse, and temperature. Blood pressure and pulse will be measured in triplicate, in the sitting position, and

should be measured prior to blood draws. The 3 sitting blood pressure measurements and 3 pulse values will be averaged and used as the value for that visit. If the measurements are less than three, the averaged values on the available data will be used.

The number and percent of patients meeting criteria for treatment-emergent abnormalities in vital signs and weight at any time during study will be summarized (SP III and SP IV separately). Treatment group comparisons will be performed using the Fisher's exact test for SP III. [Table CGAP. 5.6](#) displays the criteria used to define treatment emergent changes in vital signs and weight. The last column of the table displays the patient populations defined by baseline categories, the treatment emergent categorical changes will be analyzed for each of those patient populations for SP III. The criteria generally consist of 2 parts, an absolute threshold and a change from baseline amount. The baseline and post-baseline definitions for vital signs analyses are in [Table CGAP. 5.4](#).

Table CGAP. 5.6 Criteria for Treatment-Emergent Categorical Changes in Vital Signs

Parameter	Direction	Criteria	Patients Population defined by Baseline Categories
Systolic BP (mm Hg) (sitting)	Low	≤90 and decrease ≥20	All patients; >90; ≤90
	High	≥140 and increase ≥20	All patients; <140; ≥140
	PCS High	≥180 and increase ≥20	All Patients; <180; ≥180
	Sustained Elevation	≥140 and increase ≥20 at 2 consecutive visits	All patients; <140; ≥140
Diastolic BP (mm Hg) (sitting)	Low	≤50 and decrease ≥10	All patients; >50; ≤50
	High	≥90 and increase ≥10	All patients; <90; ≥90
	PCS High	≥105 and increase ≥15	All Patients; <105; ≥105
	Sustained Elevation	≥90 and increase ≥10 at 2 consecutive visits	All patients; <90; ≥90
Systolic BP or Diastolic BP (mm Hg) (sitting)	Sustained Elevation	Meeting criteria for systolic BP for 2 consecutive visits or meeting criteria for diastolic BP for 2 consecutive visits or both	All Patients
Pulse (bpm) (sitting)	Low	<50 and decrease ≥15	All patients; ≥50; <50
	High	>100 and increase ≥15	All patients; ≤100; >100
	Sustained Elevation	>100 and increase ≥15 at 2 consecutive visits	All patients; ≤100; >100
Weight (kg)	Low	(Loss) decrease ≥7%	All patients
	High	(Gain) increase ≥7%	All patients
Temperature (° C)	Low	<35.6° C and decrease ≥1.1° C	All patients; ≥35.6° C
	High	≥38.3° C and increase ≥1.1° C	All patients; <38.3° C

Abbreviations: BP = blood pressure; bpm = beats per minute; F = degrees Celsius; kg = kilograms; mm Hg = millimeters of mercury; PCS = Potentially Clinically Significant.

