Study I5Q-JE-CGAP (Study CGAP) is a multisite, randomized, long-term (1-year), two arms, open-label study. This study will be evaluating the safety and effectiveness of galcanezumab (120 mg/month and 240 mg/month) in the prevention of migraine headache. As shown in protocol I5Q-JE-CGAP (protocol CGAP), Japanese patients with episodic migraine (EM) will roll over from Study I5Q-JE-CGAN. In addition to these patients with EM, Japanese patients with chronic migraine (CM) will be also enrolled in the study CGAP. The objective of this addendum is to evaluate safety and effectiveness of galcanezumab in Japanese patients with CM. Schedule of Activities, Objective and Endpoints, Study Design, Study Population, Treatments, and Statistical Consideration are described in this protocol addendum (1).

4. Protocol Additions

The content below will apply to patients with CM enrolled in Study CGAP. The rest of the parts of the protocol should be referred to the main protocol.

2. Schedule of Activities

This is for the patients with CM.

Study Period (SP)	SP I- Screening	SP II- Prospective Baseline	SP	III – 7	Гrea	tmer	ıt										SP I Follo up	
(Target) Interval (days) since previous visit			30- 45	14	16	30	30	30	30	30	30	30	30	30	30	30	60	60
Allowable range (days) between visits	3-45	30-40a																
Interval allowance (days) compared from previous visit				±3	±3	±7	±7	±7	±7	±7	±7	±7	±7	±7	±7	±7	±7	±7
Visit	1	2	3ª	4	5	6	7	8	9	10	11	12	13	14	15	16/ ET	17	18/ ET
Month			0	(D14)	1	2	3	4	5	6	7	8	9	10	11	12	14	16
Assessments and	Procedures	S																
Informed consent	X																	
Inclusion/Exclusi on	X	X	X															
Demographics	X																	
Physical examination ^b	X																	
Height	X																	
Weight	X									X						X		X
Waist and hip circumference	X																	
Medical history	X																	
Pre-specified migraine history/ pre-therapy		X																
Substance use	X																	
Prior Therapy (Migraine Medication)	X																	
ECG ^c	X		X							X						X		X
Vital signs ^d	X		X		X	X	X	X	X	X			X			X	X	X
Adverse events	X	X	X	X	X	X	X	X	X	X	X	X	X	X	X	X	X	X

Study Period (SP)	SP I- Screening	SP II- Prospective Baseline	SP	SP III – Treatment							SP IV – Follow- up							
(Target) Interval (days) since previous visit			30- 45	14	16	30	30	30	30	30	30	30	30	30	30	30	60	60
Allowable range (days) between visits	3-45	30-40a																

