Treatment emergent changes in vital signs, weight, and ECGs	Safety Population with a baseline and at least 1 post-baseline observation	EM: Visit 3 CM: Low: Minimum value from Visits 1–3 High: Maximum value from Visits 1–3	Low: Minimum value from Visits 3.01–16 High: Maximum value from Visits 3.01–16
Continuous safety analyses	Safety Population with a baseline and at least 1 post-baseline observation	EM: Visit 3 CM: Last of Visits 1–3	Scheduled visits: 3 < Visits ≤ 16
Study Period III and IV combined			
Efficacy analyses	ITT Population with a baseline and at least 1 post-baseline observation	Visit 3	All Visits 3.01-18
Quality of Life analyses	ITT Population with a baseline and at least 1 post-baseline observation	Visit 3	All Visits 3.01-18

Study Period/Analysis	Patient Population	Baseline Observation	Post-baseline Observation(s)
Continuous safety analyses	Safety Population with a baseline and at least 1 post-baseline observation	EM: Visit 3 CM: Last of Visit 1- 3	All Visits 3.01-18
Treatment emergent immunogenicity	ADA follow-up cohort (See Section 5.5.12.1.6)	EM (LY120/LY120, LY240/LY240): CGAN Visit 3 EM (PLA/LY120, PLA/LY240): CGAP Visit 3 CM: Visit 3	All Visits 3.01–18
Study Period IV			
Continuous safety analyses – change from baseline to LOCF endpoint (ANCOVA)	Post-treatment Population with a baseline and at least one post-baseline observation	EM: Last of Visits 3-16 CM: Last of Visits 1-16	Last Visit: 16.01-18
FEAEs	Post-treatment Population	EM: All Visits in CGAN Visit 1 - 16. CM: All Visits 1- 16. Pre-existing condition that is still ongoing at Visit 1 should be evaluated as baseline values.	All Visits 16.01–18
Serious Adverse Events, Discontinuations due to Adverse Events	Post-treatment Population	NA	All Visits 16.01–18
Follow-up emergent abnormal laboratory values	Post-treatment Population with normal laboratory values at all nonmissing baseline visits (with respect to direction being analyzed) and who have at least 1 post-baseline observation	EM: All Visits 3- 16 CM: All Visits 1- 16	All Visits 16.01–18
Follow-up emergent changes in vital signs, weight and ECGs	Post-treatment Population with a baseline and at least 1 post-baseline observation	EM: Low: Minimum value from Visits 3–16 High: Maximum value	Low: Minimum value from Visits 16.01–18 High: Maximum value from Visits 16.01–18

Study Period/Analysis	Patient Population	Baseline Observation	Post-baseline Observation(s)

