		from Visits 3–16 CM: Low: Minimum value from Visits 1–16 High: Maximum value from Visits 1–16	
C-SSRS categorical analyses	Post-treatment Population with a baseline and at least 1 post-baseline C-SSRS assessment	EM: Recent History: CGAP Visit 3-16 All Prior History: All CGAN Visits 1-12 including lifetime ^a and All CGAP Visits 3.01-16 CM: Recent History: All CGAP Visits 1–16 excluding lifetime ^a All Prior History: All CGAP Visits 1-16 including lifetime ^a	All Visits 16.01–18
C-SSRS categorical analyses for improvement	Post-treatment Population with a baseline and at least 1 post-baseline C-SSRS assessment	EM: Last of CGAP Visits 3.01-16 CM: Last of CGAP Visits 3.01-16	Last of 16.01–18

Abbreviations: ADA = Anti-Drug Antibody; CM = chronic migraine; C-SSRS = Columbia Suicide Severity Rating Scale; EM = episodic migraine; FEAE = follow-up emergent adverse event; ITT = intent-to-treat; PPS = per protocol set; TEAE = treatment emergent adverse event.

Note: Visit 3.01 indicates the first unscheduled visit occurring after Visit 3 and prior to Visit 4. Other visits can be interpreted in a similar manner. For example, Visit 12.01 indicates the first unscheduled visit occurring after Visit 12 and prior to Visit 13. For efficacy and quality of life measures without unscheduled visits data point, Visit 3.01 indicates scheduled collection visits after visit 3.

^a Lifetime is captured in the C-SSRS visit 1 CRF (EM: CGAN visit 1, CM: CGAP visit 1).

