5.5.12.1. Categorical Safety Variables

Unless specified otherwise, the categorical safety analyses will include both scheduled and unscheduled visits. Unless otherwise specified, categorical safety analyses will only be conducted for Study Period III and Study Period IV separately.

Comparisons between treatment groups for all categorical safety measures will be made using the Fisher's exact test for Study Period III with the safety population, unless otherwise specified.

Descriptive statistics only will be presented for the treatment groups in Study Period IV with the post-treatment population.

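### On scheduled visits alone (CM schedule), a stable blood-pressure or pulse rise that starts between the Month 9 and Month 12 visits is counted as sustained in neither SP III nor SP IV

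*SAP*

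**What the plan says.** SAP Table CGAP. 5.6 (Section 5.5.12.1.3) defines sustained elevation as two qualifying visits in a row. The systolic rule is "≥140 and increase ≥20 at 2 consecutive visits", the diastolic rule "≥90 and increase ≥10 at 2 consecutive visits" and the pulse rule ">100 and increase ≥15 at 2 consecutive visits". A further row combines systolic and diastolic.

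The same section says that patients who meet the criteria "at any time during study will be summarized (SP III and SP IV separately"). Section 5.5.12.1 sets the general rule that "categorical safety analyses will only be conducted for Study Period III and Study Period IV separately", and it admits unscheduled as well as scheduled visits.

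SAP Table CGAP. 5.4 (Section 5.5.1.4) fixes the windows and baselines:
- **SP III:** post-baseline Visits 3.01–16. The CM baseline for highs is "High: Maximum value from Visits 1–3".
- **SP IV:** post-baseline Visits 16.01–18. The baseline is "CM: Low: Minimum value from Visits 1–16 High: Maximum value from Visits 1–16". For EM patients it runs over Visits 3–16.

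The protocol addendum's Schedule of Activities (Section 2) places CM vital signs at Visits 1, 3, 5 to 10, 13, 16, 17 and 18. None are scheduled at Visits 11, 12, 14 or 15.

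**The concern.** Each rule is reasonable alone; together they leave a gap. A two-visit criterion needs a second reading. Late in treatment the scheduled readings are three months apart, the next one falls in a different analysis period, and that period's baseline already contains the first raised value. A rise that appears late in the year and persists through follow-up therefore gets no sustained label in either period.

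One-year safety is the primary objective (SAP Table CGAP. 4.1). The sustained rows are what separate a persistent rise from a single high reading. The vital-signs section specifies no patient listing, whereas the ECG and laboratory sections list patients over SP III and SP IV combined.

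**Working it through.** The documents give no expected count for this category, so there is no figure to reproduce. The check applies the rules to the CM schedule.

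**Inputs.** Post-baseline vital-sign visits: 5, 6, 7, 8, 9, 10, 13, 16 (Months 1–6, 9, 12), then 17 and 18 (Months 14, 16). Criteria, windows and baselines are those in Tables 5.4 and 5.6. The illustrative values are assumptions: systolic 120 rising to a flat 145 mm Hg. Consecutive is read as consecutive visits with a vital-sign reading.

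**Result by onset, scheduled visits only:**

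| Onset | SP III | SP IV |
|---|---|---|
| By Visit 13 | Sustained (at latest Visits 13 + 16) | Not needed |
| After Visit 13, by Visit 16 | One reading: High, not sustained | Baseline 145, so Visits 17 and 18 must each reach 145 + 20 = 165; a flat 145 is not counted |
| After Visit 16, by Visit 17 | No reading | Baseline 120; sustained (Visits 17 + 18) |
| After Visit 17 | No reading | One reading; not sustained |

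The second row is the point. Its width is 12 − 9 = 3 months, and 3/12 = 25% of the treatment year.

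Diastolic 75 to 92 and pulse 75 to 105 (also assumed) give the same pattern. The SP IV baselines become 92 and 105, so Visits 17 and 18 would each need at least 92 + 10 = 102 mm Hg or 105 + 15 = 120 bpm.

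**Exceptions inside the window.** A raised unscheduled reading (for example at Visit 14.01) followed by a raised Visit 16 is sustained in SP III. A further rise to 165 at Visits 17 and 18 is sustained in SP IV; 164 is not.

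**Combined window.** Over Visits 3.01–18 against the pre-treatment baseline of 120, the flat 145 is sustained at Visits 16 + 17.

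**With measurement noise.** All inputs here are assumptions: mean systolic 122, between-patient SD 10, within-patient SD 7, onset uniform over 360 days, 400,000 simulated patients. For a 30 mm Hg rise starting after Month 9, the plan labels 0.2% sustained in SP III and 0.3% in SP IV. If Visit 17 may confirm Visit 16, the share is about 50%. It depends strongly on the size of the rise: about 11% at 20 mm Hg, 27% at 25 and 88% at 40. Over all onsets, detection at 30 mm Hg goes from 50% to 67%, but about 4.6 of those 17 points come from onsets before Month 9 that gain an extra pair of readings.

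**The case against.** A reader might infer that no rise after Month 9 can ever be labelled sustained. The documents do not support that. A rise starting between Visits 16 and 17 leaves the SP IV baseline untouched and can be confirmed at Visit 18. Unscheduled visits count, and a large enough further rise counts in SP IV.

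A reader might also infer that these patients go unseen. They do not. A raised Visit 16 reading enters the SP III High row, and in the noise model about two thirds of late 30 mm Hg rises do so. Vital signs are also modelled over SP III and SP IV combined against a pre-treatment baseline (Section 5.5.12.2 with Table 5.4), and adverse events are collected at every visit. This stands in part: the High row cannot tell a persistent rise from a single one, and the combined model describes means, not patients.

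The SP IV baseline is a deliberate convention: follow-up emergent means new or worse than everything before follow-up, and adverse events, laboratory values and C-SSRS follow it too. That is a good reason to leave the SP IV row alone. It does not supply the missing confirmation.

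Any two-visit rule leaves its last interval unconfirmable. True, but here the later readings are already scheduled and simply cannot be used.

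Finally, moving an off-drug Visit 17 reading into the SP III incidence would mix periods in a comparison made by Fisher's exact test, and would favour detection in patients who enter SP IV. This objection stands and shapes the fix.

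**Conclusion.** The gap is real but narrow. On scheduled visits in the CM schedule, a stable rise in blood pressure or pulse that is first seen at Visit 16 is labelled sustained in neither period. It covers 3 of the 12 treatment months. What is lost is the sustained label, not all trace of the patient. The noise figures show how far the size depends on assumed inputs (about 11% to 88% of late onsets recovered for rises of 20 to 40 mm Hg) and are not estimates for this trial.

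The conclusion rests on three readings:
- **No pairing across periods.** That Visit 16 cannot be paired with Visit 17 is inferred from the separate windows; the SAP does not say so for these rows.
- **Meaning of consecutive.** The SAP does not define it. If it means adjacent visit numbers, Visits 10 + 13 and 13 + 16 would not count either, and the gap would be wider.
- **Scope.** Only the CM schedule is in the documents, for about 60 of about 300 patients. The EM baseline in SP IV also runs through Visit 16, but whether EM patients have the same gap between readings cannot be established here.

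The change is worth making because it alters which patients are identified under the primary safety objective, at little cost.

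**What to change.** Keep the SP III and SP IV rows as planned. Add to SAP Section 5.5.12.1.3 one descriptive sustained-elevation summary over SP III and SP IV combined, for systolic, diastolic, the combined row and pulse. It should:
- use consecutive visits with a vital-sign reading across Visits 3.01–18, which also settles what consecutive means;
- measure the increase against the SP III pre-treatment baseline;
- flag patients whose first qualifying visit is at or before Visit 16.

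No test should be attached, and the summary should not replace the SP III incidence compared by Fisher's exact test.

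The cost is a short addition to the text and one derivation on data already scheduled. There is precedent in the SAP: Section 5.5.12.1.1 already tabulates adverse events that start on treatment and continue into follow-up.

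The limits should be stated with the table. Visit 17 is about 60 days after Visit 16 and about 30 + 60 = 90 days after the last scheduled injection at Visit 15, so rises that reverse quickly stay unconfirmed. Patients who do not enter SP IV have no extra reading. A rise first seen at Visit 18 still cannot be confirmed.

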5.5.12.1.4. Electrocardiogram Intervals and Heart Rate

Analyses of corrected QT (QTc) interval will be calculated using 2 correction formulas. The QTcF (msec) will be calculated with Fridericia's formula as $QT/RR^{1/3}$. The Large Clinical Trial Population Based QT Correction (QTcLCTPB) (msec) will be calculated with the formula as $QT/RR^{0.413}$. For the QTc calculations, the unit for QT is milliseconds and the unit for RR is seconds. For patients with QRS ≥120 milliseconds at any time during the study (including baseline and SP IV), the QTc interval (e.g., QTcF and QTcLCTPB) will be excluded from the analyses (change from baseline to LOCF endpoint analysis, categorical analysis).

A listing of Subjects with post-baseline emergent ECG findings (SP III, SP IV combined) will be created which ignore QTc related abnormality for patients with QRS \geq 120 milliseconds but include the other abnormalities such as heart rate, as well as QRS.

A listing of ECG data for patients with QRS \geq 120 milliseconds at any time during the study will be provided. (Baseline, SP III and SP IV combined)

The number and percent of patients meeting criteria for treatment emergent abnormalities in ECG intervals (PR, QRS, QTcF, and QTcLCTPB) and heart rate at any time during study will be summarized (SP III, SP IV separately). Treatment group comparisons will be performed using the Fisher's exact test for SP III.

[Table CGAP. 5.7](#) displays the criteria for treatment emergent changes in ECG intervals, heart rate and QTcLCTPB. For QTcLCTPB, the treatment emergent low and high criteria are listed by gender and age range, based on Lilly reference ranges.

- For Treatment emergent low analyses: Patients with all normal or high values at baseline (no low values) and at least one post-baseline result will be included.
- For Treatment emergent high analyses: Patients with all normal or low values at baseline (no high values) and at least one post-baseline result will be included.
- For Treatment emergent increase analyses: Patients with a baseline and at least 1 post-baseline result will be included.

The baseline and post-baseline values are summarized in [Table CGAP. 5.4](#).

Table CGAP. 5.7 Criteria for Treatment-Emergent Changes in ECG Intervals and Heart Rate

Parameter	Direction	Criteria	
Heart Rate (bpm)	Low	<50 and decrease ≥ 15	
	High	>100 and increase ≥ 15	
PR Interval (msec)	Low	<120	
	High	≥ 220	
QRS Interval (msec)	Low	<60	
	High	≥ 120	
QTcF (msec)	Low	Males: <330	Females: <340
	High	Males: >450	Females: >470
	PCS High	>500 msec	
	Increase	Increase >30 msec	
		Increase >60 msec	
Increase >75 msec			
QTcLCTPB (msec)	Low	Male (All ages): <330;	Female (All ages): <340
	High	Male Age (yrs): criteria <18: >444 18-25: >449 26-35: >438 36-45: >446 46-55: >452 56-65: >448 >65: >460	Female Age (yrs): criteria <18: >445 18-25: >455 26-35: >455 36-45: >459 46-55: >464 56-65: >469 >65: >465
	PCS High	>500 msec	
	Increase	Increase >30 msec	
		Increase >60 msec	
Increase >75 msec			

Abbreviations: msec = millisecond; PCS = Potentially Clinically Significant; QTcF = The Fridericia's corrected QT interval; QTcLCTPB = The Large Clinical Trial Population Based QT Correction; yrs = years.

In addition, summary of qualitative ECG abnormalities (SP III with Fisher's exact test and SP IV without test) will be conducted which will include summaries of 11 ECG categories (Axis, Rhythm, Conduction, Ischemia, Infarction, Injury, Morphology, U-waves, T-waves, ST Segment, and Other Abnormalities) of qualitative findings at any time post-baseline for two population:

[1] Subjects who are baseline normal for a category,

[2] Subjects who are baseline normal for all of 11 categories.

Note that the output [1] contains overall interpretation result.

For SPIII and SP IV summaries, the baseline qualitative ECG status is defined as the status at last available qualitative ECG assessment during the baseline period (EM: assessment day =Visit 3 for SP III, and assessment day <=Visit 16 for SP IV. CM: assessment day <=Visit 3 for SP III, and assessment day <=Visit 16 for SP IV). A category is a collection of possible descriptions (findings) of one qualitative aspect of an ECG. A category name is the name of the qualitative aspect of the ECG (for example, Rhythm, Conduction, Morphology, Ischemia, and so forth). A finding is 1 of the possible specific descriptions (for example, Sinus Bradycardia, Acute Septal Infarction) within a category.

Listing of Abnormal Qualitative ECG by Finding Category will be created (SP III, SP IV combined)

5.5.12.1.5. Laboratory Tests

The incidence rates of patients with treatment emergent abnormal, high, or low laboratory values based on Covance reference ranges at any time post-baseline will be assessed using the Fisher's exact test for each laboratory test for SP III and no tests for SP IV.

Patients will be defined as having a treatment emergent low value if they have all normal or high values at baseline, followed by a value below the lower reference limit at any post-baseline visit. Patients with all normal or high values at baseline (no low values) will be included in the analysis of treatment emergent low laboratory values. Patients will be defined as having a treatment emergent high value if they have all normal or low values at baseline, followed by a value above the upper reference limit at any post-baseline visit. Patients with all normal or low values at baseline (no high values) will be included in the analysis of treatment emergent high laboratory values.

For analytics simply classified as normal or abnormal, patients will be defined as having a treatment emergent abnormal value if they have all normal values at baseline, followed by an abnormal value at any post-baseline visit. Patients with all normal values at baseline will be included in the analysis of treatment emergent abnormal laboratory values.

The incidence of patients with the following elevations in hepatic laboratory tests at any time post-baseline will also be summarized and compared between treatment groups using the Fisher's exact test for SP III and no tests for SP IV.

- The percentages of patients with an alanine aminotransferase (ALT) measurement greater than or equal to 3 times (3×), 5 times (5×), and 10 times (10×) the Covance upper limit of normal (ULN) during post-baseline period will be summarized for all patients with a post-baseline value.

- The percentages of patients with an aspartate aminotransferase (AST) measurement greater than or equal to 3 times (3×), 5 times (5×), and 10 times (10×) the Covance upper limit of normal (ULN) during post-baseline period will be summarized for all patients with a post-baseline value.
- The percentages of patients with an Alkaline phosphatase (ALP) greater than or equal to 2 times (2×) the Covance ULN during post-baseline period will be summarized for all patients with a post-baseline value.
- The percentages of patients with a total bilirubin (TBIL) measurement greater than or equal to 2 times (2×) ULN during post-baseline period will be summarized for all patients with a post-baseline value.

Hy's law is defined as the combination of elevation of $ALT \geq 3 \times ULN$ and $TBIL \geq 2 \times ULN$, in the absence of significant cholestasis (i.e., $ALP < 2 \times ULN$).

The analysis of elevation in ALT, AST, ALP, and TBIL will contain 3 subsets:

- Patients whose nonmissing maximum baseline value is less than or equal to $1 \times ULN$ for ALT, AST, ALP, and TBIL.
- Patients whose nonmissing maximum baseline value is greater than $1 \times ULN$ for ALT, AST, ALP, and TBIL, and at the same time less than or equal to $2 \times ULN$ for ALT and AST, $1.5 \times ULN$ for ALP and TBIL.
- Patients whose nonmissing maximum baseline value is greater than $2 \times ULN$ for ALT and AST, $1.5 \times ULN$ for ALP and TBIL.

Note that patients with no corresponding postbaseline values will be excluded.

A listing of Subjects with abnormal Laboratory Results will be created. (SP III, SP IV combined)

A listing of Subjects with abnormal Hepatic Laboratory Results will be created. (SP III, SP IV combined)

